9. STUDY CALENDAR

Baseline evaluations are to be conducted within 2 weeks prior to start of protocol therapy. Scans and assessment of cardiac function must be done ≤ 4 weeks prior to the start of therapy. In the event that the participant's condition is deteriorating, laboratory evaluations should be repeated within 48 hours prior to initiation of the next cycle of therapy.

All assessments must be performed prior to administration of any study medication. All study assessments and medications should be administered within ± 3 days of the protocol-specified date, unless otherwise noted. After completion of the first two cycles, cycle visits and associated studies can be performed within ± 7 days of the protocol-specified date, unless otherwise noted. The study calendar for the Phase I and II portions of the study are as per the following pages:

9.1. Study Calendar: Phase I and Phase I-T

	Pre-Study	Prior to Each Cycle ^{a,o}	Cycles 1 & 2 Day 8, 15, 22 (+/- 3 days)	Every 2 Cycles	Off Treatment
Informed Consent ^a	X ^a				
Medical History	X				
Concomitant Medications ^b	X ^b	X ^b	X ^b		X ^b
Adverse Event Assessment		X	X		X
Vital Signs ^c	X ^c	X ^c	X ^c		X ^c
BP Measurement at Home (See Appendix C)		Twice a day while on study			
Physical Exam	X	X	X		X
Height	X				X
Weight	X	X			
ECOG Performance Status ^d	X ^d	X ^d			X ^d
CBC with Differential	X	X	X		X
Serum Chemistry ^e	X ^e	X ^e	X ^e		X ^e
INR and PTT	X				
Troponin T or I TSH and Free T4 ^f	X ^f	X ^f			X ^f
Urinalysis ^g	X ^g	X ^g	X ^g		X ^g
Electrocardiogram	X	X ^h			
MUGA or Echocardiogram ⁱ	X			X	
Pregnancy Test ^j	X ^j				
CA-125 Measurements ^k	X ^k	X ^k			
Tumor Measurements ^{l,m}	X ^l			X ^{l,m}	
Review of BP diary by study team		X	X		
Pharmacokinetics ^p		X	X		

- a: Informed consent will be obtained prior to any study-related screening tests. For Cycle 1 Day 1, physical examination and laboratory evaluations do not have to be repeated if they have been performed at screening within 7 days of Cycle 1 Day 1.
- b: Because of a potential for interaction of cediranib and olaparib with other drugs through the cytochrome P450 system, the Principal Investigator should be alerted if the patient is taking any other medications known to affect P450 isoenzymes.
- c: Temperature, pulse, blood pressure
- d: See Appendix A for ECOG performance status
- e: Sodium, potassium, chloride, bicarbonate, BUN, creatinine, glucose, albumin, calcium, phosphorus, AST (SGOT), ALT (SGPT), alkaline phosphatase, total bilirubin, LDH.
- f: Pre-study and prior to the first 2 cycles, then as clinically indicated, and at off-study visit.
- g: A urine protein:creatinine ratio may be used instead. See Section 6.3.3 Management of Proteinuria if dipstick at least 1+ on study.
- h: ECG done prior to Cycle 1 and 2, and then prior to every cycle if clinically indicated.

- i: MUGA or echocardiogram should be done at baseline and every other cycle for those patients at increased risk for compromised LVEF. Increased risk patients have had one or more of the following: (1) prior treatment with anthracyclines, (2) prior treatment with trastuzumab, (3) NY Heart Association classification of II, (4) prior central thoracic RT, (5) history of myocardial infarction within the 12 months prior.
- j: beta-HCG for women of childbearing potential.
- k: If patients have no measurable cancer for RECIST assessment, the patient must have two pretreatment CA-125 samples that are at least twice the upper limit of normal (at least 1 day but not more than 3 months apart; at least one of the samples should be within 1 week of starting treatment). A CA-125 level drawn just prior (within 1 week of) to Cycle 1 Day 1 of cediranib/olaparib dosing will be used as the BASELINE CA-125. CA-125 will be drawn at the start of each cycle.
- l: Tumor measurements by CT scans or MRI will be performed within the 4 weeks prior to starting cediranib/olaparib and will be performed after every 8 weeks (+/- 1 week) of treatment. If a partial or complete response is noted, a confirmatory CT scan or MRI should be performed. The next planned restaging CT scan or MRI may be used as the confirmatory scan.
- m: For patients in the Phase 1 portion of the trial who have been on trial for greater than 1 year without evidence of disease progression, the treating investigator may choose to decrease the frequency of re-staging CT scans to once every 4 cycles.
- o: For patients in the Phase 1 portion of the trial who have been on trial for greater than 3 years without evidence of disease progression, the treating investigator may choose to decrease the frequency of visits to once every 2 cycles. These patients should have CBC with differential, serum chemistry, and urine protein assessment (UPC or urinalysis) performed and con-meds, adverse events, and blood pressure diary should be reviewed in-person or by telephone with the study team, but all other assessments may be omitted.
- p: Reference section 8.14 of the protocol for further information on exact timing requirements of samples.

9.2. Study Calendar: Phase II

	Pre-Study ^a	Prior to Each Cycle ^{a,r}	Cycles 1&2 Weekly ^b	Cycles 1&2 Day 15 (+/- 3 days)	Every 2 Cycles	Every 4 Cycles	Off Treatment ^p
Informed Consent ^a	X ^a						
Medical History	X						
Concomitant Medications ^c	X ^c	X ^c	X ^c				X ^c
Adverse Event Assessment		X	X ^b				X
Vital Signs ^d	X ^d	X ^d					X ^d
BP Measurement at Home ^e (See Appendix C)		Twice a day while on study					
Physical Exam	X	X					X
Height	X						X
Weight	X	X					
ECOG Performance Status ^f	X ^f	X ^f					X ^f
CBC with Differential	X	X		X			X
Serum Chemistry ^g	X ^g	X ^g		X ^g			X ^g
INR and PTT	X						
Troponin T or I TSH and Free T4 ^h	X ^h	X ^h					X
Urinalysis ⁱ	X ⁱ	X ⁱ		X ⁱ			X ⁱ
Electrocardiogram	X ^j	X ^j					
MUGA or Echocardiogram ^k	X					X	
Pregnancy Test ^l	X ^l						
CA-125 Measurements	X	X					X
Tumor Measurements ^{m,q}	X ^m				X ^{l,q}		
Family Risk Assessment	X ⁿ						
Translational Studies	X ^o						

- a: Informed consent will be obtained prior to any study-related screening tests and within 4 weeks of starting study drug. For Cycle 1 Day 1, physical examination, laboratory evaluations, and EKG do not have to be repeated if they have been performed at screening within 7 days of Cycle 1 Day 1.
- b: Participants should be contacted at least once weekly over the phone or be assessed in person for the first two cycles on study to assess for adverse events and concomitant medications. Pre-cycle and off-study AE assessments must be done at a scheduled clinic visit.
- c: Because of a potential for interaction of cediranib and olaparib with other drugs through the cytochrome P450 system, special attention should be paid to other medications known to affect P450 isoenzymes, in particular CYP3A4. Please see Appendix D for a list of these medications.
- d: Temperature, pulse, blood pressure
- e: Home blood pressure monitoring is only required for patients receiving cediranib
- f: See Appendix A for ECOG performance status

- g: Sodium, potassium, chloride, bicarbonate, BUN, creatinine, glucose, albumin, calcium, phosphorus, AST (SGOT), ALT (SGPT), alkaline phosphatase, total bilirubin.
- h: Pre-study, prior to the first 2 cycles, and at off-study visit for all participants. Otherwise, should be checked prior to each cycle if clinically indicated.
- i: A urine protein:creatinine ratio may be used instead. See Section 6.3.3 Management of Proteinuria if dipstick at least 1+ on study.
- j: ECG done prior to Cycle 1 and 2, and then prior to every cycle if clinically indicated. The pre-study ECG may be used as the Cycle 1 ECG if performed within 7 days of Cycle 1 Day 1.
- k: MUGA or echocardiogram should be done at baseline and every 4 cycles for those patients at increased risk for compromised LVEF. Increased risk patients have had one or more of the following: (1) prior treatment with anthracyclines, (2) prior treatment with trastuzumab, (3) NY Heart Association classification of II, (4) prior central thoracic RT, (5) history of myocardial infarction within the 12 months prior.
- l: beta-HCG for women of childbearing potential.
- m: Tumor measurements by CT scans or MRI will be performed within the 4 weeks prior to starting cediranib/olaparib and will be performed after every 8 weeks (+/- 1 week) of treatment. If a partial or complete response is noted, a confirmatory CT scan or MRI should be performed. The next planned restaging CT scan or MRI may be used as the confirmatory scan. For patients in the Phase 2 portion of the trial, the frequency of restaging studies will decrease to once every 12 weeks (+/- 1 week) after the 20th cycle of treatment.
- n: The Family Risk Assessment questionnaire (Appendix I) should be completed by the patient and returned to the study staff by Cycle 2.
- o: For patients opting to participate in translational studies at the NCI. Study schedules will be as per Section 5.1.4.
- p: Off-treatment assessments should be performed within 30 days of stopping study treatment.
- q: For patients in the Phase 2 portion of the trial who have been on trial for greater than 4 years without evidence of disease progression, the treating investigator may choose to decrease the frequency of re-staging CT scans to once every 4 cycles.
- r: For patients in the Phase 2 portion of the trial who have been on trial for greater than 4 years without evidence of disease progression, the treating investigator may choose to decrease the frequency of visits to once every 2 cycles. These patients should have CBC with differential, serum chemistry, and urine protein assessment (UPC or urinalysis) performed and con-meds, adverse events, and blood pressure diary should be reviewed in-person or by telephone with the study team, but all other assessments may be omitted.

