6.3.1. Dose Modifications and Management of Cediranib and Olaparib Toxicities

General Management of Adverse Events (Non-Hematologic)	
Observation	Action
AE resolves promptly with supportive care	Maintain dose level
Any grade 2 non-hematologic AE or grade 3 fatigue related to cediranib or olaparib that persists despite maximal support.	Hold study drug(s) ¹ for up to 14 days until toxicity resolves to ≤ grade 1. ³ Treatment may be restarted at one dose level lower for the drug(s) causing the toxicity, as per the dose reduction levels in Sections 6.2.1 and 6.2.2, at the treating investigator's discretion. The overall PI of the study should be informed regarding all dose modifications. Patients whose toxicity has not resolved after 14 days will be removed from study.
Any ≥ grade 3 non-hematologic (excluding grade 3 fatigue or hypertension or easily correctable asymptomatic grade 3 laboratory abnormalities)	Hold study drug(s) ¹ for up to 14 days until toxicity resolves to ≤ grade 1. ³ Treatment may be restarted at one dose level lower for the drug(s) causing the toxicity, as per the dose reduction levels in Sections 6.2.1 and 6.2.2, at the treating investigator's discretion. The overall PI of the study should be informed regarding all dose modifications.
1. Grade 3 or 4 non-hematologic AE related to cediranib and olaparib combination that does not resolve to grade 0-2 within 14 days despite maximum supportive care after treating patient at the lowest reduced dose level. ² 2. Grade 3 or 4 non-hematologic AE related to cediranib/olaparib lasting > 14 days despite maximum supportive care and treatment being held.	Remove patient from study.

- 1 For patients receiving both cediranib and olaparib after the DLT assessment period has completed in the Phase 1 or Phase 1-T or for patients enrolled to the cediranib/olaparib arm in the Phase 2 -- if the observed AE is specifically attributed to only one of the drugs, that drug may be held while the patient continues to receive the drug not associated with the observed AE. The time a given drug is held should not exceed 14 days.
- 2 Excluding hypertension, see below 6.3.2
- 3 For thromboembolic events, treatment may be resumed at the discretion of the investigator once patient is asymptomatic. For weight loss events, treatment may be resumed at the discretion of the investigator once weight has stabilized.

Dose Modification and Management of Hematologic Adverse Events	
Observation	Action

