10. MEASUREMENT OF EFFECT

Response is not the primary endpoint of the phase I component of this trial. However, participants with measurable disease will be assessed by RECIST and those who do not have measurable cancer via clinical response benefit (modified GCIg CA-125 response or stable disease for at least 16 weeks). For the purposes of this study, participants should be reevaluated for disease response based upon how their disease is being assessed. If RECIST criteria apply, patients should undergo a repeat radiographic assessment every 8 weeks (+/- 1 week) with CT or MRI scans. For patients with only elevated CA125 values, modified GCIg CA125 response will be measured every 4 weeks (+/- 1 week). In addition to a baseline scan, confirmatory scans should also be obtained at least 4 weeks following initial documentation of objective response. The next planned restaging CT Scan or MRI may be used as the confirmatory scan.

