The expected PFS to a platinum-based regimen in this setting is approximately 6 months (Markman *et al.*, 1991). The PFS observed with cediranib alone in this patient population was 5.2 months (Matulonis *et al.*, 2009). In the Phase II study of olaparib in BRCA mutation carriers, the estimated PFS ranged from approximately 2.5 months to 5.5 months between the 100mg BID and 400mg BID cohorts (Audeh *et al.*, 2010). In BRCA wild-type patients, the estimated response rate was 23.9% (Gelmon *et al.*, 2010), which is comparable to the 20% response rate observed with single-agent cediranib (Matulonis *et al.*, 2008). Given this similar activity and the observed data in the Audeh *et al.* Phase II trial, we therefore project a PFS in a control arm of olaparib alone to be similar to that of platinum-based regimens at 6 months. An increase in progression-free survival to 10.5 months (from the projected 6 months) would be considered of clinical interest. In the Phase II portion of the study, for a power of 86% to reject H_0 : Median PFS in both arms = 6 months in favor of H_1 : Median PFS of the group with olaparib combination > 10.5 months with an alpha of 0.10, 71 events (i.e., disease progressions) out of a total of 82 evaluable patients will be required to detect a hazard ratio of 0.5716 (experimental over control). We will therefore perform the final PFS analysis when the 71st evaluable patient experiences cancer progression. It is anticipated that 10% of subjects will not be evaluable, and thus the total number of subjects with platinum-sensitive disease to be enrolled in the Phase II portion of the study is 90. Progression-free survival will be evaluated by Kaplan-Meier analysis and Log-Rank test for between group comparison, and median survival times reported. To minimize the likelihood of exposing study patients to an inactive regimen, an interim assessment of the hazard ratio for disease progression (experimental over control) will be performed when the 36th patient experiences cancer progression. If the estimated hazard ratio at that time is 1 or greater, accrual to the study will be halted for futility.

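### The Phase II calendar ties tumor scans to treatment cycles while Section 10 gives a plain 8-week interval; if scans move with dose holds and holds differ by arm, PFS is biased towards the arm with more holds

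*Combined protocol and SAP*

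**What the plan says.** The combined protocol and SAP describes the Phase II scan schedule in two ways.

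- **Section 9.2 (Study Calendar: Phase II).** Tumor measurements sit under "Every 2 Cycles". Footnote m says they "will be performed after every 8 weeks (+/- 1 week) of treatment", and later drop to "once every 12 weeks (+/- 1 week) after the 20th cycle of treatment". Footnote q allows a further reduction for patients on trial for more than 4 years, with the new interval again counted in cycles.
- **Section 10 (Measurement of Effect).** Where RECIST applies, "patients should undergo a repeat radiographic assessment every 8 weeks (+/- 1 week) with CT or MRI scans". Section 10.4.1 repeats the 8-week interval and its window. Neither mentions treatment or cycles.

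Two other parts of the protocol determine whether the difference matters. Section 5.1 sets criteria for Day 1 of each cycle (neutrophils, blood pressure, creatinine, liver tests, performance status), so a cycle start can slip. Section 6.3.1 allows holds; for patients on both drugs its first footnote says "The time a given drug is held should not exceed 14 days", and the same footnote lets one drug be held while the other continues.

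PFS runs from start of treatment to objective progression (Section 10.4.5). It is tested by log-rank (Section 14.2), with no sensitivity analysis for scan timing.

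**The concern.** Progression found by imaging is dated at the scan that shows it. A site that schedules from the calendar can reasonably count cycles or weeks on drug, and will then scan late after a hold or a delayed cycle. A site that schedules from Section 10 will not. Both would be following the protocol.

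The scan window does not absorb the difference: a 14-day hold exceeds the 1-week tolerance by 14 − 7 = 7 days.

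If delays were equally common in the two arms, they would add noise and a common shift. If they were more common in one arm, that arm's progressions would be dated systematically later. The log-rank test on the primary endpoint would then partly measure scan timing. Nothing in the planned analysis would reveal this.

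**Working it through.** **1. The plan's own figure.** Inputs from Section 14.2: "with an alpha of 0.10, 71 events (i.e., disease progressions) out of a total of 82 evaluable patients will be required"; hazard ratio 0.5716; "for a power of 86% to reject" the null. Allocation is 1:1 (Section 5). Sidedness is not stated, but the alternative is directional: "Median PFS of the group with olaparib combination > 10.5 months".

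Schoenfeld power = Φ(√d/2 × |ln HR| − z), with √71/2 × |ln 0.5716| = 4.213 × 0.5593 = 2.356.

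- One-sided 0.10: Φ(2.356 − 1.282) = Φ(1.075) = 85.9%. This reproduces the stated 86%.
- Two-sided 0.10: Φ(2.356 − 1.645) = Φ(0.712) = 76.2%. This does not.

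The check below therefore uses one-sided 0.10.

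**2. Simulation set-up.** There are 41 + 41 patients with exponential PFS, a median of 6 months in both arms under the null, uniform accrual over 18 months (Section 14.2), and analysis at the 71st event. Progression is dated at the first scan on or after it occurs. Scan k falls 8 weeks plus any hold after scan k − 1. Each scenario was run with and without a random scan shift of up to 1 week either way, using 2,500 to 4,000 trials (Monte Carlo standard error about 0.5 to 0.8 percentage points).

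**Assumed, not documented:** how often holds occur in each arm, and that each hold moves the scan clock by its full length (1 or 2 weeks).

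**3. Results with no true treatment effect** (with / without scan shift).

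| Scenario | One-sided type I error | Mean hazard ratio |
|---|---|---|
| Scans fixed every 8 calendar weeks | 10.4% / 10.9% | 1.00 / 1.00 |
| 50% of intervals held in each arm, 2 weeks | 10.3% / 10.2% | 1.00 / 1.01 |
| Combination 50%, control 25%, 1 week | 14.0% / 11.0% | 0.96 / 0.97 |
| Combination 50%, control 25%, 2 weeks | 12.4% / 11.2% | 0.98 / 0.98 |
| Control 50%, combination 25%, 2 weeks | 8.6% / 8.4% | 1.03 / 1.03 |
| Combination only, 25%, 2 weeks | 12.2% / 9.8% | 0.98 / 1.00 |
| Every combination patient held 2 weeks before first scan, no control patient held | 15.6% / 16.6% | 0.94 / 0.93 |

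In the 50% versus 25% scenarios without the scan shift, the excess over fixed scans (11.0% and 11.2% against 10.9%) is within simulation error. The excess is clear only with the shift (12.4% and 14.0% against 10.4%).

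**4. Scale.** Across scenarios with holds only or more often on the combination, its observed median exceeds control's by at most about 0.24 month (7.23 − 6.99). The planned difference is 10.5 − 6 = 4.5 months. Under the planned effect, power in those scenarios is 84.3% to 90.4%, against 85.4% / 84.7% with fixed scans.

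**The case against.** A reader might infer more: that holds do delay scans, that they do so mainly in the combination arm because it has two drugs, and that PFS is therefore biased in favour of the combination. The documents do not support that.

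- **No passage says a hold stops the scan clock, and some point the other way.** The LVEF table in Section 6.3.4 counts cycles while drug is held. In the Phase I text (Sections 5.3 and 6.2), holds appear to fall inside a cycle: cycle 1 treatment may be held up to 7 days, and losing more than a quarter of the planned cycle 1 dose is a DLT. A 7-day hold is 7/28 = 25% of a 28-day cycle. That accounting makes sense only if the cycle keeps its length. Footnote m also counts in weeks, with a window in weeks.
- **An excess of clock-stopping holds on the combination is not documented.** Many cediranib-specific rules (hypertension, proteinuria, initial persistent diarrhea) hold cediranib alone. Olaparib can then continue, so weeks on treatment still accrue. The control arm takes olaparib 400 mg BID against 200 mg BID in the combination (Section 5). Against this, some rules hold both drugs (rotator cuff injury, Section 6.3.9), and blood pressure control is a Day 1 criterion. Neither side has a rate.
- **The effect is mostly small**, and the largest figure needs an extreme pattern of holds.

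All three points stand. They remove any claim about direction and limit the size. They do not remove the disagreement between Section 9.2 and Section 10, or the lack of a statement on scans during a hold. The LVEF table and the Phase I text are indirect evidence on a point that the calendar words differently.

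**Conclusion.** The plan gives two clocks for the scans that date its primary endpoint and does not say which applies during a hold or a delayed cycle start. If scans follow treatment and hold frequency differs by arm, PFS is biased towards the arm with more holds. Which arm that would be is not established.

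At assumed hold rates of 50% (combination) and 25% (control), one-sided type I error is about 11% to 14%, against 10.4% to 10.9% with fixed scans, and the mean null hazard ratio is about 0.96 to 0.98. The bias vanishes with equal holds and reverses (about 8.5%, hazard ratio 1.03) when the rates are swapped. These figures rest on assumed hold rates and on every hold moving the scan clock by its full length. A bias of this size could not by itself produce the design hazard ratio of 0.5716. The point is a low-cost improvement, not evidence that the comparison is invalid.

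**What to change.** In Section 9.2 (the table column and footnotes m and q) and in Section 10, state that Phase II tumor assessments take place every 8 calendar weeks (+/- 1 week) in both arms, regardless of holds, delays or cycle number. Count from the PFS time origin, which Section 10.4.5 currently sets at start of treatment. Counting from randomisation would create a new mismatch unless the PFS definition changed too.

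Express the later interval changes in calendar time as well. With 28-day cycles, the end of cycle 20 is 20 × 4 = 80 weeks, and four cycles are 4 × 4 = 16 weeks. (The 28-day length is stated under the Phase I heading of Section 5; Section 5.1.4 and the pill diaries also use it.)

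For data already collected, add a PFS sensitivity analysis that either assigns progression to the scheduled scan date or treats it as interval-censored between scans.

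Cost: a wording change, some scans falling mid-cycle, and one extra analysis. In the simulation, fixed calendar scans leave no systematic bias (mean null hazard ratio 1.00).
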